10 REPORTING ADVERSE EVENTS

10.1 Safety Parameters and Definitions

Safety assessments will consist of monitoring and recording protocol-defined AEs and SAEs; measurement of protocol-specified hematology, clinical chemistry, and urinalysis variables; measurement of protocol-specified vital signs; and other protocol-defined events of special interest that are deemed critical to the safety evaluation of the study drug.

10.1.1 Adverse Events

For this protocol, an adverse event (AE) is any untoward medical occurrence in a subject, temporally associated with the use of study intervention, whether or not considered related to the study intervention.

An AE can therefore be any unfavorable and unintended sign (including an abnormal laboratory finding), symptom, or disease (new or exacerbated) temporally associated with the use of study intervention.

Events meeting the AE definition include:

- Exacerbation of a chronic or intermittent pre-existing condition including either an increase in frequency and/or intensity of the condition.
- New conditions detected or diagnosed after study intervention administration even though it may have been present before the start of the study.
- Signs, symptoms, or the clinical sequelae of a suspected drug-drug interaction.

Events not meeting the AE definition include:

- Any clinically significant abnormal laboratory findings or other abnormal safety assessments which are associated with the underlying disease, unless judged by the investigator to be more severe than expected for the subject's condition.
- The disease/disorder being studied or expected progression, signs, or symptoms of the disease/disorder being studied, unless more severe than expected for the subject's condition.
- Medical or surgical procedure (eg, endoscopy, appendectomy): the condition that leads to the procedure is the AE.
- Situations in which an untoward medical occurrence did not occur (social and/or convenience admission to a hospital).
- Anticipated day-to-day fluctuations of pre-existing disease(s) or condition(s) present or detected at the start of the study that do not worsen.

Page 78

10.1.1.1 Bleeding and Suspected Bleeding Events

All bleeding events and suspected bleeding events, regardless of the need for exogenous FVIII therapy as treatment, should be captured in subject diaries and recorded on the designated bleeding eCRF. Bleeding events and suspected bleeding events should not be reported as adverse events, with the following exception:

• All bleeding events and suspected bleeding events which meet one or more of the criteria for being serious (refer to Section 10.2) should be reported as serious adverse events (whether or not they are bleeding events that are normal sequelae of hemophilia, and whether or not they required exogenous FVIII as treatment).

10.2 Serious Adverse Events

A serious adverse event (SAE) is any untoward medical occurrence that, at any dose:

- Results in death
- Is life-threatening

Note: Life-threatening refers to an event in which the subject was at risk of death at the time of the event. It does not refer to an event, which hypothetically might have caused death, if it were more severe.

• Requires inpatient hospitalization or prolongation of existing hospitalization

Note: In general, hospitalization signifies that the subject has been detained (usually involving at least an overnight stay) at the hospital or emergency ward for observation and/or treatment that would not have been appropriate in the physician's office or outpatient setting. If the investigational product preparation, infusion, and post-infusion observation period require transfer to an inpatient setting for completion, in the absence of an AE, this will not be considered an SAE.

Complications that occur during hospitalization are AEs. If a complication prolongs hospitalization, the event is serious.

Hospitalization for elective treatment of a pre-existing condition that did not worsen from baseline is not considered an AE.

- Results in persistent or significant disability or incapacity
- Is a congenital anomaly or birth defect in the child or fetus of a subject exposed to IP prior to conception or during pregnancy
- Is an important medical event or reaction that, based on medical judgment, may jeopardize the subject or require medical/surgical intervention to prevent one of the other outcomes listed above (eg, anaphylaxis)

Page 79

10.2.1 Events of Special Interest (EOSI)

The following EOSI need to be reported to the Sponsor within 24 hours of site awareness, irrespective of seriousness, severity or causality:

- Elevation of ALT ≥1.5x ULN or ALT > ULN & >2x baseline value, regardless of whether that elevation triggers an initiation or modification of oral corticosteroid treatment
- Thromboembolic event
- Systemic hypersensitivity, anaphylactic, or anaphylactoid reactions (refer to Appendix 1)
- Development of anti-FVIII inhibitory antibodies (inhibitors)

10.3 Methods and Timing for Capturing and Assessing Safety Parameters

10.3.1 Adverse Event Reporting Period

The study AE reporting period is as follows:

- After informed consent but prior to initiation of study drug, only SAEs associated with any protocol-imposed interventions will be collected. AEs occurring during this time period should be recorded on the Medical History eCRF.
- After informed consent is obtained and following infusion of study drug, the reporting period for all non-serious AEs and SAEs begins and continues for approximately 5 years or until study discontinuation/termination, whichever is longer.

The criteria for determining, and the reporting of SAEs is provided in Section 10.2.

10.3.2 Eliciting Adverse Events

Care will be taken not to introduce bias when detecting AEs and/or SAEs. Open-ended and non-leading verbal questioning of the subject is the preferred method to inquire about AE occurrences. The Investigator will record all relevant AE/SAE/EOSI information in the subject's medical record and AE Case Report Form (eCRF).

10.3.3 Assessment of Seriousness, Severity, and Causality

The Investigator responsible for the care of the subject or medically qualified designee will assess AEs for severity, relationship to study drug, and seriousness (refer to Section 10.2 for SAE definitions). These assessments must be made by a study clinician with the training and authority to make a diagnosis (eg, MD/DO, physician's assistant, nurse practitioner, or DDS).

Page 80

10.3.3.1 Seriousness

The Investigator will assess if an AE should be classified as "serious" based on the seriousness criteria enumerated in Section 10.2. Seriousness serves as a guide for defining regulatory reporting obligations.

10.3.3.2 Severity

Severity (as in mild, moderate, or severe headache) is not equivalent to seriousness, which is based on subject/event outcome or action criteria usually associated with events that pose a threat to a subject's life or functioning. The Investigator will determine the severity of each AE, SAE and EOSI using the NCI CTCAE v4.03. Adverse events that do not have a corresponding CTCAE term will be assessed according to the general guidelines for grading used in the CTCAE v4.03 as stated in Table 10.3.3.2.1.

Table 10.3.3.2.1: Adverse Event Grading (Severity) Scale

Grade	Description	
1	Mild: asymptomatic or mild symptoms; clinical or diagnostic observation indicated	ons only; intervention not
2	Moderate: minimal, local or noninvasive intervention indicated; limiting instrumental activities of daily living (ADL) ^a	g age-appropriate
3	Severe or medically significant but not immediately life-threatening: hospitalization or prolongation of hospitalization indicated; disabling; limiting self-care ADL ^b	
4	Life threatening consequences; urgent intervention indicated	Grade 4 and 5 AEs
5	Death related to AE	should always be reported as SAEs

^a Instrumental ADL refer to the following examples: preparing meals, shopping for groceries or clothes, using the telephone, managing money.

10.3.3.3 Causality

The Investigator will determine the relationship of an AE to the study drug and will record it on the source documents and AE eCRF. To ensure consistency of causality assessments, Investigators should apply the guidance in Table 10.3.3.3.1.

^b Self-care ADL refer to the following examples: bathing, dressing and undressing, feeding oneself, using the toilet, taking medications, not bedridden.

Page 81

Table 10.3.3.3.1: Causality Attribution Guidance

Relationship	Description	
Not Related	Exposure to the IP has not occurred OR	
	The administration of the IP and the occurrence of the AE are not reasonably related in time	
	OR	
	The AE is considered likely to be related to an etiology other than the use of the IP; that is, there are no facts, evidence, or arguments to suggest a causal relationship to the IP.	
Related	The administration of the IP and the occurrence of the AE are reasonably related in time	
	AND	
	The AE could possibly be explained by factors or causes other than exposure to the IP	
	OR	
	The administration of IP and the occurrence of the AE are reasonably related in time	
	AND	
	The AE is more likely explained by exposure to the IP than by other factors or causes.	

Factors suggestive of a causal relationship could include (but are not limited to):

- Plausible temporal relationship
- Absence of alternative explanations
- Rarity of event in a given patient or disease state
- Absence of event prior to study drug exposure
- Consistency with study product pharmacology
- Known relationship to underlying mechanism of study drug action
- Similarity to adverse reactions seen with related drug products
- Abatement of AE with discontinuation of study drug, and/or recurrence of AE with reintroduction of study drug

The Investigator's assessment of causality for individual AE reports is part of the study documentation process. Regardless of the Investigator's assessment of causality for individual AE reports, the Sponsor will promptly evaluate all reported SAEs against

Page 82

cumulative product experience to identify and expeditiously communicate possible new safety findings to Investigators and applicable regulatory authorities.

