The fallback procedure will be used to adjust for multiplicity of the two interim analyses at Week 26 and the final analysis at Week 52 (regardless of the interim analyses results, the study is planned to continue upon the DMC's recommendation, and the final analysis will be performed at Week 52). At the final analysis at Week 52, the secondary efficacy endpoints will be tested hierarchically; the level of significance will be determined by the fallback procedure.

The secondary and tertiary endpoints will be summarized descriptively at the interim (Week 26) analyses.

The details of the interim analyses, including the control of Type I error rate, will be specified in the SAP.

Analysis of safety endpoints will be primarily descriptive. The incidence of AEs will be summarized by system organ class, preferred term, relationship to study drug, seriousness, and severity. Clinical laboratory test values, vital signs, vector shedding and immune response parameters will be summarized descriptively by visit.

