9.3.3.1 Study Safety Evaluation Criteria

If any of the following events occur in a subject in the study who has received BMN 270 infusion, an urgent evaluation by the DMC will be required and further enrollment into the trial will be temporarily put on hold if recommended by the DMC per Section 9.1.

- 1. Liver dysfunction (criteria do not apply to ALT elevations with an extra-hepatic etiology):
 - \circ ALT > 5x ULN, for more than 2 weeks
 - \circ ALT > 3x ULN and (total bilirubin > 2x ULN or INR >1.5)
 - \circ ALT > 3x ULN with signs and symptoms of liver dysfunction
- 2. The occurrence of Grade 4 or Grade 5 adverse events assessed as related to study drug (events of liver dysfunction are defined above).
- 3. The occurrence of an AE of hepatic failure.
- 4. The detection of high-titer neutralizing antibodies (>5 BU) to hFVIII following BMN 270 infusion in two subjects.
- 5. The occurrence of any cancer (except non-melanoma skin cancer) at any point after BMN 270 infusion.
- 6. The occurrence of a thromboembolic event with FVIII activity > 150 IU/dL in one subject.

If any of the following events occurs in a subject in the study who has received BMN 270 infusion, an urgent evaluation by the DMC will be required. Further enrollment into the trial will continue while DMC evaluation is ongoing, unless deemed otherwise by the DMC:

- 1. The detection of high-titer neutralizing antibodies (>5 BU) to hFVIII following BMN 270 infusion in one subject.
- 2. Occurrence of a thromboembolic event in one subject.

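### The causality table lets a timely adverse event with a likely other cause, and nothing beyond timing pointing to the IP, be coded either 'Related' or 'Not Related'

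*Protocol*

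**What the plan says.** Section 10.3.3.3 (Amendment 4) sets out one table with a stated aim: "To ensure consistency of causality assessments, Investigators should apply the guidance in Table 10.3.3.3.1".

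- **'Related', first route.** Two conditions joined by AND. One is a reasonable time relation between infusion and event. The other reads: "The AE could possibly be explained by factors or causes other than exposure to the IP".
- **'Related', second route.** The same time relation, and the IP is the more likely explanation.
- **'Not Related'.** Three alternatives joined by OR. The first is no exposure and the second is the lack of a reasonable time relation. The third reads: "The AE is considered likely to be related to an etiology other than the use of the IP". This third line is then glossed: "that is, there are no facts, evidence, or arguments to suggest a causal relationship to the IP".

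Below the table is a list of factors suggestive of causality. It includes a plausible time relation and the absence of other explanations.

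The relationship code is used in two places:

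- **AE summary.** The Synopsis states: "The incidence of AEs will be summarized by system organ class, preferred term, relationship to study drug, seriousness, and severity". Amendment 4, Section 14.6, also plans a summary by relationship.
- **Urgent DMC evaluation.** Section 9.3.3.1 lists as a trigger: "The occurrence of Grade 4 or Grade 5 adverse events assessed as related to study drug". Amendments 4 and 6 both carry it.

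**The concern.** The first 'Related' route appears to be misworded. It is satisfied by the presence of some cause other than the IP and does not ask whether the IP could have caused the event. It also sets no limit on how probable the other cause may be. The third 'Not Related' line deals with events whose other cause is likely and says nothing about timing. Whatever is likely is also possible, so the two definitions can meet on the same event, and no precedence rule is given.

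Two investigators following the table correctly could then code the same event differently. This is a single-arm study at about 60 sites, with no concurrent control rate against which inconsistent attribution would cancel. The related-AE incidence would partly reflect which line was read, and so would the question of whether a Grade 4 or 5 event meets the DMC trigger.

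**Working it through.** The plan states no figure on this point, so there is none to reproduce. The check is whether the two definitions exclude each other.

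**Coding the table.** For an exposed subject, let:
- T = reasonably related in time
- A = another cause is possible
- L = another cause is likely (implies A)
- M = the IP is the more likely explanation (excludes L)
- E = nothing suggests the IP as cause (excludes M)

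Then Related = (T and A) or (T and M). Not Related = (not T) or line 3.

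**Admissible combinations.** For each value of T:
- L = 0 leaves 2 values of A and 3 pairs (M, E): 2 × 3 = 6.
- L = 1 forces A = 1 and M = 0 and leaves 2 values of E: 2.

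That is 8 per value of T, and 2 × 8 = 16 in all.

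**Three readings of line 3.**

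| Reading | Line 3 | Meets both definitions |
|---|---|---|
| (a) gloss ignored | L | 2 of 16: every case with T = 1 and L = 1 |
| (b) gloss binding | L and E | 1 of 16: T = 1, A = 1, L = 1, E = 1 |
| (c) gloss binding, and timing itself counts as an argument for the IP, so T excludes E | L and E | 0 of 13 |

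Under (c) the total is 8 for T = 0. For T = 1 it is 2 × 2 = 4 with L = 0 and 1 with L = 1, so 8 + 5 = 13.

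The counts are of logical combinations, not of events; they show where the definitions collide, not how often.

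**What the readings show.** Reading (a) drops half of the line, so (b) is the fair literal reading. Under (b) one class stays double-coded: timely, likely other cause, nothing else pointing to the IP. Only (c) removes it. Under (c) line 3 can apply only when T = 0, which line 2 already covers, so line 3 does no work. The table does not state (c).

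**Internal consistency of the first 'Related' route.** The factor list counts the absence of other explanations in favor of causality; the first route is met when another explanation exists. Section 9.4.8.2 offers an illustration: an ALT rise with a simultaneous CPK rise after hard exercise is treated as plainly unrelated to BMN 270. If that rise were reasonably related in time to the infusion, the first route would make it 'Related', because exercise could explain it. The illustration concerns the first route only. ALT rises are common after this product, so some investigators would find a further argument for the IP.

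**The case against.** The strongest reply has three parts.

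**The gloss and the factor list.** The gloss defines the third 'Not Related' line, so a likely other cause is not enough; nothing may point to the IP. The list below the table names a plausible time relation as suggestive of causality. A timely event then always has one argument for the IP, line 3 fails, and the event is 'Related' only. A redundant line is not a contradiction.

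The first step stands and narrows the overlap. A reader might infer that every timely event with a likely other cause meets both definitions, but where anything beyond timing suggests the IP, the event is 'Related' only. The second step is a possible reading. The table nowhere says that timing alone defeats line 3, and an investigator who gives that line a function will read it otherwise.

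**The version.** The wording is from Amendment 4. Amendment 6 as shown ends at Section 10.3.2. Its list of tables keeps Table 10.3.3.3.1. Its change summary reports an added attribution to corticosteroids or other immunosuppressants, plus minor edits for consistency and clarity, and no rewording of IP causality. Persistence is probable but cannot be confirmed.

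**The safety net.** In the Amendment 4 text, Grade 4 and 5 events are always SAEs (Table 10.3.3.2.1), and SAEs go to the sponsor within 24 hours whatever the causality call (Section 10.5.1). The sponsor evaluates all of them regardless of that call (Section 10.3.3.3), and the DMC reviews individual safety data continuously (Section 15). Amendment 6 states that enrollment is complete, so the possible enrollment hold no longer matters. All of this stands. It does not recode the investigator's field, and the sponsor's SAE evaluation does not reach non-serious events, which also enter the incidence summary.

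**Conclusion.** The point holds in a limited form. As worded in Amendment 4, the table permits either code for a timely event with a likely other cause and nothing beyond timing pointing to the IP. It leaves open whether timing alone counts as an argument for the IP. The related-AE incidence is therefore inconsistently defined, chiefly for non-serious events, and the related Grade 4/5 trigger depends partly on wording. The remaining consequence of that trigger is the urgent DMC evaluation itself.

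The conclusion assumes that the gloss binds and that the wording survives into Amendment 6.

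Three stronger inferences are not supported:

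- **A numerical range for the related count.** No document gives the share of events in the overlap, so any range would rest on an invented proportion.
- **That the related-AE rate cannot be interpreted at all.** The ambiguity is confined to one class of events, and AEs are also summarized by class, term, seriousness and severity.
- **That some timely events fit neither category.** In the coding above this needs T = 1, A = 0 and M = 0: no other cause even possible, yet the IP not the more likely explanation. That is hardly a real event.

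**What to change.** 1. Reword the first 'Related' route so that exposure to the IP must be a possible explanation of the event, even though other factors could also explain it.
2. State whether a time relation alone counts as evidence for the IP, so that the categories exclude each other. If it counts, remove or rewrite the third 'Not Related' line, which could then never apply to a timely event. If it does not, say that events meeting that line are 'Not Related' despite their timing.
3. Check the Amendment 6 text of Section 10.3.3.3 and make the change there if the wording persists.

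The cost is one table line, one added sentence and a note to about 60 sites. AE collection runs for about 5 years (Section 10.3.1), so later events would still benefit. Events already coded would stand under the old wording, so the report should state when the definition changed. Presenting already-coded events both ways is optional and feasible only if an alternative cause was recorded, which the text shown does not establish. No endpoint, dose or treatment rule is affected.

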10.4 Procedures for Recording Adverse Events

10.4.1 Recording Adverse Events on a eCRF

Investigators should use precise medical terminology when recording AEs or SAEs on the AE eCRF. Avoid colloquialisms and abbreviations.

Record only one diagnosis, sign, or symptom per event field on the AE eCRF (eg, nausea and vomiting should not be recorded in the same entry, but as 2 separate entries).

In order to classify AEs and diseases, preferred terms will be assigned by the Sponsor to the original terms entered on the AE eCRF, using MedDRA (Medical Dictionary for Regulatory Activities) terminology.

10.4.1.1 Diagnosis versus Signs and Symptoms

The Investigator will attempt to establish a diagnosis of the event based on signs, symptoms, and/or other clinical information. Whenever possible, the diagnosis (not the individual signs/symptoms) will be documented as the AE/SAE. Using accepted medical terminology, enter the diagnosis (if known). If not known, enter sign(s) and/or symptom(s). If a diagnosis subsequently becomes available, then this diagnosis should be entered on the AE (or SAE, as appropriate) eCRF, replacing the original entries where appropriate.

10.4.1.2 Adverse Events Occurring Secondary to Other Events

In general, AEs occurring secondary to other events (eg, cascade events) should be identified by their primary cause. For example, if severe diarrhea is known to have resulted in dehydration, it is sufficient to record only diarrhea as an AE or SAE on the AE eCRF. However, medically important events that may be linked and/or separated in time should be recorded as independent events on the AE eCRF. For example, if severe hemorrhage leads to renal failure, both events should be recorded separately on the AE eCRF.

10.4.1.3 Persistent or Recurrent Adverse Events

A persistent AE (duration of adverse event > 7 days) is one that extends continuously, without resolution, between subject evaluation time points. Events that change in severity necessitate the recording of an additional AE. AEs that do not have a change in severity should be recorded only once on the eCRF.

A recurrent AE is one that occurs and resolves between subject evaluation time points, but then subsequently recurs. All recurrences of the AE should be recorded on the AE eCRF.

Page 83

For example, if a subject has an adverse event of ALT increased that subsequently resolves, but the subject's ALT increases again, that should be reported as two adverse events – the initial ALT increase, and the second ALT increase.

